### 14.2 Analysis of Endpoints

All data will be tested for normality. Where data are not normally distributed a nonparametric test will be performed. Data will be presented as means  $\pm$  SD. Statistical analyses will be performed on SPSS software version 22.0 (Chicago, IL). Statistical difference will be accepted when  $P < 0.05$ . Statistical differences will be assessed by repeated-measures

ANOVAs. Where baseline differences are present, analyses of covariance (ANCOVAs) will be used with baseline as a covariate.

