### 6.2 Secondary Objectives

Secondary objectives: 1) Does CBJ reduce perceived discomfort and pain; 2) is our protocol acceptable to individuals with RP (i.e. cold water stimulus, CBJ palatability) and feasible to perform in a future multi-centre randomised control trial (RCT); and 3) to establish recruitment and retention rates. Resulting estimated effect sizes in relation to their confidence intervals from our primary objective(s) measures will be utilised to identify our primary outcome measure and to power a larger, definitive, multi-centre randomised, control trial.

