## 7. STUDY DESIGN

### 7.1 Summary of Study Design

The proposed study will be a pilot, randomised placebo-controlled, double-blind, crossover trial. The effect of acute and chronic CBJ supplementation on microvascular function in people with RP will be compared to a placebo (CBJ with the nitrates removed). The placebo is the same in colour, odour, texture and taste as CBJ (Mark [name] et al., 2014) but does not cause an increase in plasma nitrate or nitrite ([name] et al., 2016). The volunteers will be given a full briefing about the study and given the participant information sheet before we seek their written consent (see below). The individual's severity of RP symptoms will be established according to the International Consensus Criteria for Diagnosing RP (Maverakis et al., 2014).

*Participants and Recruitment:* Twenty-five individuals with RP would need to be recruited in order to estimate a moderate to large effect size in a pilot study (Johanson & Brooks, 2009). Therefore, we aim to recruit 30 individuals (at a rate of 1 per week) with RP to account for a 15% drop-out rate (typically seen in our clinical trials). Participants will be recruited from a database of known individuals with RP who attend outpatient clinics at the Queen Alexandra Hospital (Portsmouth) and via posters and word of mouth within the University of Portsmouth. The participants will attend the lab on five occasions during which cold sensitivity and endothelial function (iontophoresis) will be assessed (Spinnaker Building, University of Portsmouth).

*Consent and Screening:* Visit 1 will act as a screening, consent and baseline assessment (3.5-4 hours).

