#### 14.3 Procedure for Dealing with Missing, Unused and Spurious Data

Where statistic differences are present, post hoc (Bonferroni-corrected) analysis will be performed. Outliers will remain within the data. Within the data analysis software missing data will be coded 9999 and the data point missed during analysis.

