## **20. DISSEMINATION AND OUTCOME**

RP can cause significant discomfort and pain to individuals during a vasospasm. Dietary nitrate appears to offer a simple, low cost means of modifying blood flow to the peripheries and, ultimately, reducing both the discomfort and pain experienced by individuals with RP. This study will also advance our understanding of the aetiology and pathophysiology of RP, specifically the role that the nitrate-nitrite-nitric oxide pathway might play in modulating RP symptoms. An understanding of the effects of concentrated beetroot juice on microvascular blood flow and pain may lead to a range of simple, low cost and effective therapeutic interventions to prevent and treat episodes of RP.

Results (estimates of effect sizes and confidence intervals) from this pilot study will be utilised to define our primary outcome and to power a larger, definitive multi-centre randomised control trial with our co-applicants and collaborators around Europe. Once our final report has been submitted to Scleroderma and Raynaud's UK, we will apply for NIHR funding via a researcher-led Research for Patient Benefit (RfPB) or an Efficacy and Mechanism Evaluation (EME) bid (depending on the effect size and sample size) and or a Horizon 2020 collaboration bid. The results will be disseminated through publication in peer-reviewed scientific and clinical journals and via presentations, local, national and international meetings. A summary of the results will be sent to all the participants. Finally, an open day and presentation will be carried out where the participants will be informed of

the study findings and have the opportunity to ask any pertinent questions and/or provide feedback.

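### A normality pre-test chooses between ANOVA and an unnamed nonparametric test, and neither branch specifies the effect size with confidence interval that the pilot is meant to deliver

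*Combined protocol and SAP*

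**What the plan says.** The governing rule is in section 14.2 of the combined protocol and SAP: "All data will be tested for normality. Where data are not normally distributed a nonparametric test will be performed". It does not name the normality test or its level. It does not say whether raw values, within-person differences or residuals are tested, or which nonparametric test follows.

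The default is also in 14.2: "Statistical differences will be assessed by repeated-measures" ANOVAs, at a 0.05 threshold. Baseline enters only conditionally: "Where baseline differences are present, analyses of covariance (ANCOVAs) will be used with baseline as a covariate". No period, sequence or carry-over term is named, and no transformation is planned. Descriptive results are means and SDs, and no effect estimate or interval is specified for either branch. Section 14.3 adds "Outliers will remain within the data", so extreme values feed the pre-test. Section 14.4 says that no SAP beyond this is needed.

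The design is a crossover (section 7.1: "The proposed study will be a pilot, randomised placebo-controlled, double-blind, crossover trial"). On what it must deliver, section 6.2 says "Resulting estimated effect sizes in relation to their confidence intervals from our primary objective(s) measures will be utilised to identify our primary outcome measure" and that they will power the definitive trial. Section 20 repeats this: "Results (estimates of effect sizes and confidence intervals) from this pilot study will be utilised to define our primary outcome".

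**The concern.** The pilot exists to estimate effects and to choose among candidate outcomes. A rule under which the data pick the method, outcome by outcome, works against that in three ways.

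- Skin blood flow and cutaneous vascular conductance are positive, ratio-type measures and plausibly right-skewed. They are therefore the outcomes most likely to be sent to the nonparametric branch.
- The usual rank tests for paired or repeated data (Wilcoxon signed-rank, Friedman) take no covariate and have no place for period. No estimate is planned to accompany them.
- Skin temperature might stay with ANOVA while flow goes to ranks, or the acute and chronic contrasts of one outcome might part ways. The effects that section 6.2 wants compared would then come from different methods.

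At stake is the choice of primary outcome for the definitive trial and the inputs to its sample size.

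**Working it through.** **The plan's own figure.** Section 9 gives 25 evaluable participants and 15% drop-out. 25 / (1 − 0.15) = 29.4, rounded up to 30, which matches the recruitment target. The 25 itself cannot be rebuilt, because no SD, effect in units or power is stated. n = 25 is used below.

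**Assumptions.** The documents give no SD, CV or skewness for any outcome. Assumed here: log-normal flow data, four post-dose visits (2 to 5), Shapiro-Wilk at 0.05, two-sided tests at 0.05. All simulations used 2,000 to 4,000 runs per setting, so the Monte Carlo standard error is at most √(0.25/2000) = 1.1 percentage points.

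**Step 1: how often the pre-test rejects.** With CV as the input, log SD = √ln(1 + CV²) and within-person log correlation 0.5 to 0.7:

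| CV | One raw variable | Any of four raw visits | One paired difference |
|---|---|---|---|
| 0.2 | 15–17% | 44–49% | 8–9% |
| 0.5 | 58–59% | 92–95% | 25–27% |
| 0.8 | 86% | over 99% | 49–52% |
| 1.0 | 93% | about 100% | 60–65% |

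With within-person log SD 0.3 and between-person log SD 0.3 to 0.8, at least one of four raw visits fails in 92–99.7% of trials, and a paired difference fails in 23–73%. Truly normal data fail 5% of the time for one variable and about 16–19% for any of four.

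**Step 2: mixed routes.** At between-person log SD 0.3 a paired difference fails in about 23% of trials. If the acute and chronic contrasts are tested separately and roughly independently, they take different routes in 2 × 0.23 × 0.77 = 35%. Direct simulation gave about a third.

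**Step 3: what the method changes.** Power for one CBJ–placebo contrast, 22% true increase, within-person log SD 0.3, between-person 0.3 to 0.8:

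| Analysis | No period effect | Period effect equal to treatment effect |
|---|---|---|
| Raw paired t, no pre-test | 40–58% | not tabulated |
| Section 14.2 rule (Wilcoxon as fallback) | 52–60% | 41–45% |
| Log scale, no period term | 62–63% | about 49% |
| Log scale with period term | 61–63% | about 60% |

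The last column takes 13 participants on CBJ first and 12 on placebo first, with responses higher in period 2. With the odd participant in the other sequence, the rule gives close to 50%. Type I error is about 5% for both the rule and the log-scale, period-adjusted contrast.

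**Step 4: precision and cost of the period term.** The 95% CI half-width, in SDs of the paired difference, is t(24)/√25 = 2.064/5 = 0.413 without period. With it, for a 12/13 split, it is t(23) × 0.5 × √(1/12 + 1/13) = 0.414. Without the term, the treatment contrast absorbs (n₁ − n₂)/n of any period effect: 4% at 13/12, 12% at 14/11, 20% at 15/10.

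On the log scale the CBJ/placebo ratio would be known to within a factor of about 1.10–1.13 at CV 0.3, 1.16–1.22 at CV 0.5 and 1.25–1.34 at CV 0.8. For within-person log SD 0.3 the factor is exp(0.414 × 0.3 × √2) = 1.19.

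**The case against.** A reader might infer more than the documents support. Five points on the other side stand.

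- **The pre-test does not remove a period adjustment.** None is named in the plan. Its absence is a gap in both branches.
- **Baseline adjustment is lost only where the conditional ANCOVA would have applied.** A single visit 1 baseline is also the same for both treatments within a person, so it largely cancels from the within-person contrast.
- **The rule does not strip out a planned effect size with interval.** The ANOVA branch of 14.2 specifies none either. Means and SDs are presented whatever the normality result, and a Hodges-Lehmann estimate with interval could accompany a signed-rank test. The plan simply does not ask for one.
- **Diversion to ranks is not shown to be almost certain.** That needs assumed skew plus the reading that every raw visit must pass. The phrase in 14.2 does not say raw values, and on paired differences the chance is far lower.
- **The pre-test alone does not cost power.** The rule matches or beats always running a raw paired t-test (52–60% against 40–58%), and type I error is not inflated. Power is also a secondary yardstick in a pilot for which section 7.2 declares no primary outcome.

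These points narrow the concern without removing it. The method still depends on the data, the fallback is unnamed, no estimate is attached to either branch, and section 14.4 rules out a later document that would settle it.

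**Conclusion.** The point holds in limited form. Section 14.2 leaves the method for each outcome to a normality pre-test, and it does not say how the effect sizes and intervals required by 6.2 and 20 will be obtained in either branch. Rejection is likely for skewed flow data: about 23–73% on paired differences and 92% or more on the any-of-four-visits reading.

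A prespecified log-scale, period-adjusted analysis would raise power by a few to about ten points with no period effect, and by about 15 to 19 points (from 41–45% to 60%) with a period effect as large as the treatment effect. The gain comes from the log scale and the period term; deleting the pre-test would not achieve it by itself.

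Every frequency and power figure rests on assumed log-normality and assumed SDs. The gaps in the wording do not. This should be changed, but it does not threaten the validity of the trial.

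**What to change.** Replace the pre-test rule in 14.2 with one prespecified analysis per outcome:

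- Analyse flow and conductance on the log scale, reported as a CBJ/placebo ratio with 95% CI. Analyse temperature on the raw scale, reported as a difference with 95% CI.
- Fit treatment, visit type (acute or chronic), their interaction and period as fixed effects, with participant as a random effect.
- Check residuals by plot. Give a rank-based result only as a sensitivity analysis, with the test named in advance.
- State that these estimates and intervals are the ones used to choose the primary outcome under 6.2.

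The cost is wording and slightly different code. The period term costs almost no precision (0.414 against 0.413 SD). The downside is that flow results are read as percentage changes rather than in measurement units.

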#### 14.3 Procedure for Dealing with Missing, Unused and Spurious Data

Where statistic differences are present, post hoc (Bonferroni-corrected) analysis will be performed. Outliers will remain within the data. Within the data analysis software missing data will be coded 9999 and the data point missed during analysis.

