## 9. SAMPLING

Twenty-five individuals with RP would need to be recruited in order to estimate a moderate to large effect size in a pilot study (Johanson & Brooks, 2009). Therefore, we aim to recruit 30 individuals (at a rate of 1 per week) with RP to account for a 15% drop-out rate (typically seen in our clinical trials). We will utilise an opportunistic sampling process, from both clinics and posters and word of mouth.

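### Section 14.3 makes post hoc comparisons conditional on a significant ANOVA, with Bonferroni over an undefined family, and Section 14 names no ungated CBJ-minus-placebo estimate at the acute and chronic visits

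*Combined protocol and SAP*

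**What the plan says.** Section 14.2 sets the inferential method: "Statistical differences will be assessed by repeated-measures" ANOVAs, with significance at P < 0.05. It uses ANCOVA where baselines differ and a nonparametric test where data are not normal, and it presents data as means and SD. It does not state the ANOVA's factors or levels.

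Section 14.3 then adds: "Where statistic differences are present, post hoc (Bonferroni-corrected) analysis will be performed". The number and identity of these comparisons are not given. Section 14.4 says that no SAP is needed beyond this text, so no later document is promised to settle it.

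Section 7.1 sets two treatment questions, CBJ against placebo after acute dosing and after chronic supplementation. Section 6.2 states what the answers are for: "Resulting estimated effect sizes in relation to their confidence intervals from our primary objective(s) measures will be utilised to identify our primary outcome measure". Sizing the definitive trial is the other stated use. Section 20 likewise describes the results as effect-size estimates with confidence intervals. Neither section makes these depend on a significant test.

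On size, Section 9 says: "Twenty-five individuals with RP would need to be recruited in order to estimate a moderate to large effect size in a pilot study". It gives no numerical effect, SD, power or precision.

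**The concern.** The pilot has two planned questions per measure, but the only step in Section 14 that explicitly provides for follow-up comparisons sits behind a significance condition. It then carries a correction whose size depends on a family nobody has defined. If that family is all pairs of visits, most of the correction is spent on pairs that answer no stated question, such as acute placebo against chronic CBJ.

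Two things are at stake. A test of the contrast of interest loses power by an amount that cannot be read from the plan. More important for a pilot, Section 14 does not say how the estimates promised in Sections 6.2 and 20 will be computed. An analyst who followed Section 14 literally could finish without a CBJ-minus-placebo estimate and interval for measures whose ANOVA was not significant. Those estimates are needed to compare candidate primary outcomes on equal terms.

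**Working it through.** **The plan's own figure.** Section 9 sets 30 as the recruitment target: "we aim to recruit 30 individuals (at a rate of 1 per week) with RP to account for a 15% drop-out rate". 25/(1 − 0.15) = 29.4, rounded up to 30, so it reproduces. The 25 cannot be derived, because no SD, effect, power or precision is given.

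**Inputs.** From the documents: n = 25 and level 0.05. Assumed: two-sided tests (sidedness is not stated), and a standardised paired difference d (mean CBJ-minus-placebo difference divided by its SD) of 0.5 for moderate and 0.8 for large. Section 9 says only "estimate a moderate to large effect size in a pilot study".

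**Family sizes, m.** The text fixes none, so I took three:
- m = 2: CBJ against placebo at the acute visits and at the chronic visits.
- m = 6: all pairs of the four supplementation visits, 4 × 3/2.
- m = 10: all pairs of the five visits, 5 × 4/2.

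**Bonferroni alone.** For a two-sided paired t test, power is P(|T| > t_c). T is noncentral t with 24 degrees of freedom and noncentrality d√25 = 5d, and t_c is the two-sided critical value at level 0.05/m.

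**Gate plus Bonferroni.** I simulated a repeated-measures ANOVA at 0.05 followed by the paired contrast at 0.05/m. The data were normal with compound symmetry, the SD of the paired difference was 1, and there were no period or carryover effects. Layouts were one-way with four levels, one-way with five levels, and 2×2 (treatment by acute/chronic). The effect was present either at both visit types or at the chronic visits only.

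| Rule | d = 0.5, ungated | d = 0.5, gated | d = 0.8, gated |
|---|---|---|---|
| Direct contrast, no gate, no correction | 67% | – | 97% (ungated) |
| m = 2 | 55% | 50-54% | about 94% (92% in the 2×2 layout with a chronic effect only) |
| m = 6 | 37% | 37% | 86% |
| m = 10 | 30% | 30% | about 81% |

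Relative to 67%, the gated figures at d = 0.5 are 0.50/0.67 to 0.54/0.67 = 0.75 to 0.81 for m = 2, 0.37/0.67 = 0.55 for m = 6, and 0.30/0.67 = 0.45 for m = 10. With m = 6 or 10 almost all of the loss comes from Bonferroni. The gate on its own, without correction, leaves 57-66%. Holm over the two planned contrasts, ungated, gives 56-62%.

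**The 2×2 main effect.** Averaging two independent paired differences, each with SD 1, gives an SD of 1/√2 = 0.71. If both effects are 0.5, the standardised effect is 0.5/0.71 = 0.71 and power is about 92-93%. If only the chronic effect exists, it is 0.25/0.71 = 0.35 and power is about 40%.

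**Estimates.** At a true 0.50 the mean estimate over all trials is 0.50, and Bonferroni does not move a point estimate. If estimates were kept only after a significant one-way ANOVA, the mean would be 0.53-0.57. If they were kept only after a significant all-pairs post hoc test, it would be 0.69-0.71. The sample size a later trial needs is proportional to 1/d². Sizing on these values would give (0.50/0.57)² = 0.77 to (0.50/0.53)² = 0.89 of the required number in the first case, and (0.50/0.71)² = 0.50 to (0.50/0.69)² = 0.53 in the second. Both cases require selective reporting.

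**The case against.** The strongest defence is that Section 14.3 conditions post hoc tests, not effect sizes. Sections 6.2 and 20 plan effect sizes with confidence intervals and attach no significance condition. A reader might infer that contrasts will exist only for significant outcomes, and that the pilot will therefore hand inflated effects to the definitive trial. The documents do not support this. Inflation needs a rule that drops non-significant estimates, and no such rule is written. This part of the defence stands.

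A reader might also infer that the rule roughly halves power. That needs an all-pairs family, which the text never states, and a moderate effect. With two corrected contrasts the loss at 0.5 SD is about a fifth to a quarter, and at 0.8 SD no reading comes near halving. Skin measures are taken throughout the cold challenge and as a dose response to acetylcholine (Section 10.4), so the post hoc step may concern time points or doses instead. This also stands.

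In a 2×2 ANOVA the treatment main effect tests CBJ against placebo with no post hoc step, and with high power if both effects exist. That is correct, but it averages the acute and chronic effects and so does not answer the two questions separately.

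Finally, no power target is stated and the sample size is justified by estimation, so lost power breaches nothing in the plan. That is right, and it makes the missing estimates the more important half of the point. None of these arguments supplies the missing specification: each relies on a factor structure, family or reporting rule that Section 14 leaves open.

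**Conclusion.** The point holds as a mismatch between the written analysis and the pilot's stated product. Section 14 gates and corrects post hoc comparisons over an undefined family, and does not commit to reporting CBJ minus placebo at the acute and chronic visits with intervals.

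Every gated post hoc reading examined loses power for a visit-specific contrast. At n = 25 and 0.5 SD the loss runs from 67% to between 54% and 30%. At 0.8 SD it is modest, from 97% to between 94% and 81% in the one-way layouts. These figures rest on assumed effect sizes, two-sided tests, normal data with compound symmetry, and no period or carryover effect. They are not a breach of any stated power. Bias in the effect sizes is a conditional risk that the present wording fails to exclude; it is not something the plan prescribes.

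**What to change.** Replace the post hoc sentence in Section 14.3 with: *For each primary-objective measure, CBJ minus placebo at the acute visits and CBJ minus placebo at the chronic visits will be estimated as two planned contrasts from the same model, with 95% CIs, and reported whatever the overall F test. If error control is wanted, Holm is applied to the tests of these two contrasts only.* State the ANOVA's factors and levels in Section 14.2, and label any other visit, time-point or dose comparison as exploratory.

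The change is wording only, with the same data and software. It carries out what Sections 6.2 and 20 already promise. The price is less multiplicity protection over comparisons that answer no stated question, which is small for a pilot whose purpose is estimation.

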## 14. DATA ANALYSIS

### 14.1 Description of Analysis Populations

This is a pilot study. All participants who complete all 5 visits will be entered into the analysis as per protocol.

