### 15. ETHICS

NHS Local Research Ethics Committee (REC) approval will be obtained prior to commencement of the study. The REC, local NHS, research and development department and all site specific forms and patient identification centre forms will be forwarded to SRUK prior to recruitment of participants. Written informed consent will be obtained from all participants. Insurance indemnity will be provided by the UoP for this study.

Every effort has been made to keep the risks and discomforts to a minimum but there are some risks associated to taking part. Not all volunteers will experience any or all of the risks stated below, but participants will be made aware of them.

The main burden to participants is a significant lifestyle alteration because of a change in dietary practices for two, two week periods. This will involve drinking 70ml of either nitrate rich beetroot juice or nitrate depleted beetroot juice on a daily basis for two, two week periods.

We will also be asking people with RP to put their hand and foot into 15°C water as part of the cold sensitivity test. This may cause some discomfort associated with RP. We will be measuring the rewarming and temperature of the hands and feet. Participants will be reminded that they are free to withdraw at any time point.

Other less burdensome tests will be performed such as:

Blood pressure; participants will feel a cuff squeeze their arm and this can be uncomfortable for a few moments. Blood samples: Intravenous access can cause discomfort associated with insertion of the needle. We will take a blood sample on four occasions. Iontophoresis may cause some local discomfort/itching sensation during the delivery of acetylcholine and sodium nitroprusside, however this is transient occurring only when the current is applied (8 x 20 s).

A well-recognised side effect of beetroot consumption is that it may turn urine and faeces red. This is not harmful and will pass rapidly after discontinuation of the juice. Subjects will be told of this during the consent visit. Subjects will also be asked to refrain from using anti-bacterial mouthwashes for a week before drinking the juice and during the intervention itself. This is critical as it interferes with the biological pathway in which we believe this intervention works.

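### A five-visit completer with one empty cell for an outcome drops out of that outcome's repeated-measures ANOVA, although 14.3 says only the missing value is left out

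*Combined protocol and SAP*

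**What the plan says.** Three short sections of the combined protocol and SAP bear on this.

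- **14.1, analysis populations:** "All participants who complete all 5 visits will be entered into the analysis as per protocol".
- **14.2, analysis of endpoints:** "Statistical differences will be assessed by repeated-measures" ANOVAs, run in SPSS 22. If groups differ at baseline, "analyses of covariance (ANCOVAs) will be used with baseline as a covariate"; if data are not normal, a nonparametric test is used. The SPSS procedure is not named.
- **14.3, missing data:** "Within the data analysis software missing data will be coded 9999 and the data point missed during analysis".

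Section 14.4 says that no SAP beyond this text is needed, so no later document is due to settle the handling. No imputation, mixed model, statement on listwise deletion or expected missing rate appears anywhere. Sections 6.2 and 20 say that effect sizes with their confidence intervals will be used to pick the primary outcome of the definitive trial and to power it.

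**The concern.** A conventional repeated-measures ANOVA needs a full set of within-person cells. In the usual SPSS repeated-measures procedure, a value declared missing takes the participant out of that ANOVA, not just the value. Someone can attend all five visits, qualify under 14.1, have one failed laser Doppler reading or thermal image, and be absent from the analysis of that outcome. That is not what 14.3 describes.

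This is separate from drop-out. Missed visits are already dealt with by the completer rule in 14.1. The issue is a failed measurement at an attended visit, which the plan foresees, since 14.3 gives a rule for it.

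Two things are at stake. The first is precision: values already collected from a completer are discarded, in a trial with almost no spare participants. The second is comparability: the candidate outcomes are to be ranked on effect size and interval, and each could rest on a different subset, partly reflecting which measurement failed less often.

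**Working it through.** **Inputs from the documents**
- Section 9: "Twenty-five individuals with RP would need to be recruited in order to estimate a moderate to large effect size in a pilot study"; 30 are to be recruited, allowing for 15% drop-out.
- Section 7.1: supplementation visits 2, 3, 4 and 5, so 4 within-person cells with one value per visit. If baseline is added as a covariate (14.2), a fifth value can be missing.
- Section 10.4: dose response is determined separately at each site, so sites do not multiply the cells.
- Section 15, on discomfort from iontophoresis: "this is transient occurring only when the current is applied (8 x 20 s"). If each of 8 applications were a within-person level, there would be 4 × 8 = 32 cells per site.

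**Assumptions, because the documents are silent**
- Missing rate per cell, m: 1%, 2% or 5%.
- Empty cells occur independently.
- Intervals are two-sided at 95% (14.2 gives P < 0.05 without sidedness).

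**Step 1. The plan's own figure.** 25 / (1 − 0.15) = 29.4, rounded up to 30, which reproduces the stated number. Conversely, 30 × 0.85 = 25.5, so the expected reserve above 25 is half a participant.

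**Step 2. Participants kept.** With c cells, expected n = 25 × (1 − m)^c.

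**Step 3. Interval width.** For a within-person contrast, in SD units of that contrast, the half-width is t(0.975, n − 1) / √n, with n rounded to a whole number. At n = 25 it is 0.413.

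| Cells | m | Expected n | Half-width relative to n = 25 |
|---|---|---|---|
| 4 | 1% | 25 × 0.961 = 24.0 | 0.422 / 0.413 = 1.02 |
| 4 | 2% | 25 × 0.922 = 23.1 | 0.432 / 0.413 = 1.05 |
| 4 | 5% | 25 × 0.815 = 20.4 | 0.468 / 0.413 = 1.13 |
| 5 (baseline covariate) | 5% | 25 × 0.774 = 19.3 | 1.17 |
| 32 (upper-end assumption) | 1% | 25 × 0.725 = 18.1 | 0.497 / 0.413 = 1.20 |

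**Step 4. How easily it occurs.** With 4 cells and 1% missing, the chance that at least one of 25 completers is dropped from a given outcome is 1 − 0.99^100 = 1 − 0.366 = 63%.

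**Step 5. Clustered failures.** If a whole test fails at 1% of visits, rather than single pulses failing independently, the 32-cell case becomes 25 × 0.99^4 = 24.0, not 18.1.

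**Step 6. Is widening certain?** In 20,000 simulated trials (25 completers, 4 cells, 5% missing, equal between- and within-person variance), among trials that lost anyone the interval was wider in 91%, by 12.5% on average over all of them. In 9% it was narrower, because the sample SD happened to fall.

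**Step 7. What the alternative recovers.** In 300 simulated trials under the same settings, a random-participant model with treatment and acute/chronic terms gave a treatment standard error about 1.03 times the complete-data value when only empty cells were left out. It was about 1.11 times when whole participants were dropped.

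**The case against.** The best defence is that the three sections conflict only when a cell is empty, and nothing in the documents says how often that will be. With no missing values, nothing changes. This stands, and the point is worded conditionally for that reason.

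Next, 14.2 names the software but not the procedure, and 14.3 may mean only that 9999 is declared as a missing code so that it is not read as a measurement. Section 14.1 can likewise be read loosely: entering the analysis need not mean appearing in every ANOVA. These readings are possible. But under them the plan does not say what happens to a completer with an empty cell, and 14.4 closes off a later SAP that would. The text needs the same repair.

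A reader might infer that completers will certainly be lost, that every primary measure will fall below 25 and that every interval will widen. The documents do not support this. Only an outcome and site with an empty cell is affected, the descriptive means and SDs can still use all values, and widening is an expectation.

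A reader might also take about 18 of 25 as the likely size of the loss. That figure needs three things the documents do not state: that pulse is a within-person factor rather than summarised once per visit, that all 8 applications belong to acetylcholine (section 15 mentions them for acetylcholine and sodium nitroprusside together), and that failures are independent. It is an upper-end scenario.

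Finally, it is tempting to say that people with poor perfusion would be lost selectively. No passage shows this. No loss of power is claimed either, since section 9 justifies 25 for estimation and sets no power target.

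**Conclusion.** The point holds in conditional form. Where a five-visit completer has an empty cell for an outcome, the ANOVA named in 14.2, run in the usual SPSS way, drops that person from that analysis, contrary to 14.3 and to the natural reading of 14.1.

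With one value per visit, the expected loss is about 1, 2 or 5 of 25 completers at 1%, 2% or 5% missing per cell. That is modest at low rates and noticeable at 5%. It rests on assumed missing rates and on independence. Losses would be larger if many serial values per visit entered the model as separate cells, and smaller than the 32-cell figure if failures cluster within a test. Because the drop-out allowance leaves almost nothing above 25, and because the intervals are there to choose and power the next trial, the point deserves correction even at the lower figures.

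**What to change.** **14.2.** Replace repeated-measures ANOVA with a linear mixed model (SPSS MIXED) that uses all available observations. Include fixed effects for treatment, acute/chronic, their interaction, period and sequence, and a random participant effect. State a covariance structure for any serial measurements within a visit. If baseline remains a covariate, say how a missing baseline value is handled, because the model alone would still leave that participant out.

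**14.3.** Keep the rule that only the missing value is omitted, which the mixed model makes true. Declare 9999 as a missing code, and add that the participant stays in the analysis.

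**Reporting.** Give the number of participants and of values behind each estimate. For any nonparametric test that needs complete sets, report the n used.

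If the team prefers to keep the ANOVA, the minimum is to state whole-participant deletion openly and report n for each analysis.

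The cost is a wording change in two sections and a little more analysis work, with no new data. The small downside is that a covariance structure has to be chosen. The model does not remove bias if a measurement fails for reasons tied to the value that would have been observed.
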